6.7 MRI Testing, Echocardiogram, and PET Scan

All recorded MRI testing, Echocardiogram, and PET scan results captured in the CRF will be listed as part of CSR Appendix 16.2.

7 EXPLORATORY

All exploratory analyses will be described in a separate plan.

8 CHANGES FROM PROTOCOL

The Per Protocol dataset is defined in the protocol as: a subset of the Evaluable Dataset comprised of subjects who have no Major Protocol Deviations. All failed eligibility criteria are considered a Major Protocol Deviation, however, not all eligibility criteria failures should automatically remove a subject from the Per Protocol dataset. This SAP clarifies which protocol deviations will exclude a subject from the per protocol dataset and all protocol deviations will be reviewed by the study team prior to database lock to identify the final Per Protocol dataset definition.

Blood pressure values that constituted an AESI were at the discretion of the PI. As such, ranges for blood pressures of special interest (BPSI) were identified and will be analyzed according to section 6.3.

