8.1 SPECIFICATION OF SAFETY PARAMETERS

8.1.1 DEFINITION OF ADVERSE EVENTS (AE)

Per 21 CFR 312.32(a) an AE is any untoward (unfavorable, harmful, or pathologic) medical occurrence in a subject administered a medicinal (investigational) product even if the event does not necessarily have a causal relationship with this treatment.

An AE can therefore be any unfavorable and unintended sign (including an abnormal laboratory finding that is deemed clinically significant), symptom, or disease temporally associated with the use of a medicinal (investigational) product whether or not related to the medicinal (investigational) product.

An AE does include any:

- Exacerbation of a pre-existing illness
- Subjective or objective symptoms spontaneously offered by the subject and/or observed by the investigator or study staff
- Increase in frequency or intensity of a pre-existing episodic event or condition

- Condition detected or diagnosed after study drug administration even though it may have been present prior to the start of the study (unless it can be demonstrated by medical record review that the onset of the event preceded the date/time of Informed Consent)
- Continuous persistent disease or symptoms present at baseline that worsen following the start of the study
- Symptoms associated with disease not previously reported by the subject
- Lack of efficacy in the acute treatment of a life-threatening disease
- Untoward medical occurrences considered by the investigator to be related to study-mandated procedures
- Abnormal assessments (e.g., change on physical examination, ECG findings), if they represent a clinically significant finding, that were not present at Baseline or worsened during the course of the study
- Laboratory test abnormalities, if they represent a clinically significant finding, symptomatic or not, which were not present at Baseline or worsened during the course of the study

An AE DOES NOT include a/an:

- Elective medical or surgical procedure (e.g., surgery, endoscopy, tooth extraction, transfusion)
- Pre-existing diseases or conditions present or detected at the start of the study that do not worsen
- Situations where an untoward medical occurrence has not occurred (e.g., hospitalization for cosmetic elective surgery, social and/or convenience admissions)
- The disease or disorder being studied or sign or symptom associated with the disease or disorder unless more severe than expected for the subject's condition

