8.4.3 ADVERSE EVENTS OF SPECIAL INTEREST

The following will be considered adverse events of special interest (AESI):

- Clinically-significant peripheral edema or pulmonary edema.
- Systolic blood pressure (BP) < 90 or > 160 mm Hg and/or diastolic BP < 60 or > 100 mm Hg, or a change of > 25% from Day 1 (Visit 3) pre-infusion systolic and/or diastolic BP.
- Reduced kidney function (eGFR < 45 mL/min/1.73 m²).
- Suspected transmission of blood-borne infectious agents.

AESI occurring during the study should be reported within 48 hours of observation or learning of the event, unless the event is serious, in which case the event must be reported according to the timeframes specified in [Section 8.4.2.1](#).

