10.4.4 SAFETY ANALYSES

Safety, tolerability, and feasibility will be evaluated by examining the occurrence of AEs, including Treatment-Emergent AEs, and AEs leading to discontinuation from the study. AEs will be summarized by severity and by study drug dose.

Actual and changes from baseline in clinical laboratory measurements and vital signs will also be assessed and summarized. Abnormal values will be determined and flagged in the listings. Laboratory shift tables or graphics displaying the change (number of subjects) relative to the reference range from baseline to each study visit may also be presented for each test. The investigator should exercise his or her medical and scientific judgment in

deciding and documenting whether an abnormal laboratory finding, or other abnormal assessment is clinically significant.

Per-subject extent of exposure will be listed.

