2.3 Study Phase, Visit, and Day

The study is set up as shown above, along with assigned study period, visit, and day. In general, the baseline is defined as the last assessment before the first intake of the study medication unless otherwise specified. All scheduled assessments after first administration of study drug will be used.

Repeat/unscheduled assessments will not be used in descriptive statistics or any per-time point analyses but will be shown in listings as applicable. Pre-dose unscheduled assessments will be taken into account for baseline determination and post first dose unscheduled assessments will be taken into account for worst-case determination as applicable.

Reference date refers to the start date of the first study drug administration. All efficacy and safety assessments at all visits will be assigned a day relative to this date. The relative day will be defined as: visit date – reference date + 1 for visits on or after the reference date and visit date – reference date for visits before the reference date. Consequently, there is no 'Day 0' defined.

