2.6 Descriptive Summaries

All tabulated summaries will include the two treatment groups [REDACTED] and overall (includes data from both treatment groups). For endpoints that are continuous in nature: number of observations, mean, median, minimum and maximum, and standard deviation (SD) values will be presented as descriptive summary. For endpoints that are categorical in nature: frequency counts and percentages will be presented in the descriptive summary.

The number of decimal places to display for calculated data will be determined by the original scale of the data. Means, medians, and confidence intervals will be reported with one (1) additional decimal place. Standard deviation will be reported with two (2) additional decimal places. Minimum and maximum will be reported with the same number of significant digits as the method of capture.

For all efficacy and safety tables summarizing change from baseline, the baseline and post-baseline results at all planned timepoints will be included.

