6.3 Vital Signs

Summary statistics will be presented for the actual values and change from baseline values (as appropriate) at each time point for all vital signs (Temperature, Pulse Rate, Systolic Blood Pressure (BP), Diastolic BP, Respiratory Rate) and weight. Changes from baseline for all vital sign parameters and weight will include pre-dose at Day 1 to pre-dose at subsequent days and at all timepoints during infusion (Table 14.3.3.1). In addition, changes from baseline for all vital sign parameters will include pre-dose at each infusion day to all post-dose timepoints within each infusion day (Table 14.3.3.2).

The incidence of the following categorized blood pressure values and changes from baseline will be summarized (Table 14.3.3.3):

- Systolic BP > 180
- Systolic BP > 200
- Systolic BP < 90
- Diastolic BP > 110
- Diastolic BP > 120
- Diastolic BP < 50
- An absolute change of >30% from Day 1 pre-dose (baseline) in systolic and/or diastolic BP. This change includes positive and negative percent changes.

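### Table 14.3.3.3 counts measured blood pressure at only one of the five limits in protocol 8.4.3; add the other four, and state in SAP 8 what defined a blood pressure AESI and from when

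*SAP*

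**What the plan says.** Protocol 8.4.3 includes among its AESI "Systolic blood pressure (BP) < 90 or > 160 mm Hg and/or diastolic BP < 60 or > 100 mm Hg", and also a change of more than 25% from the Day 1 (Visit 3) pre-infusion value in either component. In that list the clinical-significance qualifier is attached to edema, not to BP.

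SAP 8 states: "Blood pressure values that constituted an AESI were at the discretion of the PI". It then says that ranges for blood pressures of special interest were chosen and will be analysed under SAP 6.3. That section sends seven categories to Table 14.3.3.3: SBP >180, >200 and <90; DBP >110, >120 and <50; and "An absolute change of >30% from Day 1 pre-dose (baseline) in systolic and/or diastolic BP", counted in both directions.

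The other planned BP outputs are:
- **Event tables.** Tables 14.3.1.1.1-3 and 14.3.1.5.2 (AESI) and 14.3.1.7.1-3 (BP preferred terms) count reported, coded adverse events.
- **Summary statistics.** Tables 14.3.3.1 and 14.3.3.2 summarise values and changes by timepoint. SAP 2.6 fixes the content for continuous measures: "number of observations, mean, median, minimum and maximum, and standard deviation (SD) values will be presented as descriptive summary".
- **Listing 16.2.9.** It holds the individual readings.

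On unscheduled readings, SAP 2.3 says "Repeat/unscheduled assessments will not be used in descriptive statistics or any per-time point analyses", but also that "post first dose unscheduled assessments will be taken into account for worst-case determination as applicable".

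**The concern.** The primary objective is safety and tolerability at two dose levels, and change in vital signs is a secondary safety endpoint. Protocol 2.3.1 names hypotension, particularly with rapid infusion, as a risk. Both doses are infused over 2 to 3 hours, so at equal duration the higher dose runs at 250/100 = 2.5 times the average flow rate. BP excursions by dose are therefore among the comparisons a reader of the final report will look for.

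The protocol itself says which excursions are of special interest. As planned, the full number of subjects per dose beyond four of those five limits can be known only from the events sites reported, or by counting a listing by hand.

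Reported events are an uncertain substitute. The protocol's revision history shows that the numeric BP limits arrived in Version 5.0, in place of a descriptive item on blood volume and fluid shifts. The same log refers to 24 subjects already dosed, against about 40 planned (24/40 = 60%). Event-based AESI counts may therefore mix two definitions, and SAP 8 adds investigator discretion on top.

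**Working it through.** The plan gives no figure to reproduce. The check compares the two sets of limits, asks whether another output fills the gap, and sizes the gap with assumed Day 1 values.

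**Step 1. Limits side by side** (protocol 8.4.3; SAP 6.3).

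| Item | Protocol | Nearest SAP row | Band with no row at its limit |
|---|---|---|---|
| Low SBP | <90 | <90 | none |
| High SBP | >160 | >180 | 161-180 |
| Low DBP | <60 | <50 | 50-59 |
| High DBP | >100 | >110 | 101-110 |
| Change from Day 1 | >25% | >30% | above 25%, up to 30% |

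One of five matches. Each of the other SAP rows is nested inside its protocol limit, so it gives a floor for the number beyond that limit, not the number itself.

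**Step 2. Do other outputs fill the gap?** Event tables depend on what was reported. In Table 14.3.3.1 the minimum and maximum can show that an absolute limit was passed at a scheduled timepoint, but not by how many subjects, and unscheduled readings are left out. SAP 6.3 plans change, not percent change, in Tables 14.3.3.1 and 14.3.3.2, so the 25% limit cannot be read from either. Shift tables are planned for laboratory tests and physical examination, not vital signs. Listing 16.2.9 gives no count.

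**Step 3. Readings that meet a protocol limit but no SAP category** (whole mm Hg; Day 1 values are assumptions, not trial data). A subject is in no SAP row only if every reading stays inside the SAP window. The window edges are the tighter of the absolute SAP limit and Day 1 x 0.7 or x 1.3. The protocol's change limit is Day 1 x 0.75 or x 1.25.

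- Day 1 120/70. SBP window 90-156 (120 x 1.3 = 156); a protocol limit is met at 151-156 (120 x 1.25 = 150). DBP window 50-91 (70 x 1.3 = 91); met at 50-59 and 88-91 (70 x 1.25 = 87.5).
- Day 1 140/80. SBP window 98-180 (140 x 0.7 = 98); met at 98-104 (140 x 0.75 = 105) and 161-180. DBP window 56-104 (80 x 0.7 = 56; 80 x 1.3 = 104); met at 56-59 and 101-104.
- Day 1 150/90. SBP window 105-180 (150 x 0.7 = 105); met at 105-112 (150 x 0.75 = 112.5) and 161-180. DBP window 63-110 (90 x 0.7 = 63); met at 63-67 (90 x 0.75 = 67.5) and 101-110.

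**Step 4. Two single readings.**
- 140/80 to 178/102: 178/140 = 1.271 and 102/80 = 1.275. Three protocol limits are met (SBP, DBP, change) and none of the seven SAP categories.
- 120/70 to 165/85: 165/120 = 1.375. Two protocol limits are met (SBP, change). The SAP counts the subject, but only under change above 30%.

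**The case against.** The strongest reply is that nothing was promised. Protocol 10.1 and 10.4.1 leave analytical detail to the SAP. For vital signs, protocol 10.4.4 asks for a summary and adds "Abnormal values will be determined and flagged in the listings". Reporting triggers and table categories serve different purposes, and SAP 8 discloses its ranges under changes from protocol. No stopping rule depends on the table. All of this stands, and it is why the point is an improvement and not a breach. Disclosure, however, neither restates the protocol limits nor gives a reason for these particular wider ones, and a listing is not a count.

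A reader might infer that SAP 8 flatly contradicts protocol 8.4.3, or that sites ignored fixed limits. The documents do not support that. Under protocol 8.1.1 abnormal assessments are adverse events "if they represent a clinically significant finding, that were not present at Baseline or worsened during the course of the study", and protocol 10.4.4 leaves clinical significance to the investigator. Discretion over which readings became reported events is compatible with 8.4.3. Nor were the numeric limits in force throughout, given their arrival in Version 5.0; the SAP's past tense fits that history. What stands is that SAP 8 says none of this, so its meaning has to be guessed.

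A reader might also infer that no planned table counts anyone beyond the four limits. That goes too far: every subject in the >180, >110, <50 or >30% rows is beyond the matching protocol limit and is counted. What is missing is the intermediate bands, and with them the totals.

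**Conclusion.** The concern holds in this form. Table 14.3.3.3 uses one of the protocol's five BP limits and four wider ones. Subjects whose readings all stay between the two sets fall in no row, and the total per dose beyond each of the four limits is not planned. Because each wider row is nested, the table can only undercount crossings of the protocol limits, never overcount them.

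The size in subjects is unknown. The bands in the working rest on assumed Day 1 values and show only that the gap can include readings meeting several protocol limits at once. That AESI event counts mix definitions is a possibility raised by the revision history and SAP 8, not an established fact. The incidence of treatment-emergent adverse events, a primary endpoint, is not affected. Which limits are clinically right is outside this point. It is a cheap, worthwhile change in a trial whose first aim is safety by dose.

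**What to change.** Add four rows to Table 14.3.3.3: SBP >160, DBP >100, DBP <60, and change >25% from Day 1 pre-infusion in either component. Keep the SAP's seven categories alongside.

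- Derive the rows from recorded vital signs for all Safety Set subjects, whichever protocol version they entered under, so that one rule applies to everyone.
- Include unscheduled readings after the first dose, as SAP 2.3 allows for worst-case determination.
- Report number and percentage of subjects by dose and by period. SAP 6.3 refers only to incidence and should say that subjects, not readings, are counted.
- Show how many subjects were already beyond each absolute limit at Day 1, so that pre-existing values are not read as effects of dosing.

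Reconcile SAP 8 with protocol 8.4.3 by stating what applied: from which protocol version the numeric limits were in force, and whether investigators judged which readings were reported as adverse events. It should not say that the limits were fixed from the start.

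The cost is four rows, a Day 1 column and a short clarification, from data already collected; SAP 10 allows tables to be modified with the sponsor's approval. The downside is a longer table and higher displayed counts, some from subjects beyond a limit before dosing, which the Day 1 column makes visible.

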Table 14.1.4.2	Baseline Assessment of Columbia-Suicide Severity Rating Scale (C-SSRS)	SAF
Table 14.1.4.3	APOE Genotype	SAF
Table 14.1.5.1	Medical History	SAF
Table 14.1.5.2	Social History	SAF
Table 14.1.5.4	Exercise-Activity Level	SAF
Table 14.1.5.5	Tobacco Use	SAF
Table 14.1.5.6	Alcohol and Illicit Substance Use	SAF
Table 14.1.6.1	Prior Medication	SAF
Table 14.1.6.2	Concomitant Medication	SAF
Table 14.1.7.1	Exposure to Study Drug	SAF
Table 14.1.7.2	Actual infusion rate at each time point per infusion day	SAF
Table 14.1.7.3	Numbers of below, within and above the designated infusion rate reference	SAF
Table 14.1.7.4	Overall infusion parameters per infusion day	SAF
Table 14.1.8.1	Completion of Study Drug	SAF
Table 14.1.8.2	Number of subjects completing 5 and 10 infusions	SAF
Table 14.1.9.1	Number of subjects completing 8 weeks after receiving at least 5 infusions	SAF
Table 14.1.9.2	Number of subjects completing 24 weeks after receiving at least 10 infusions	SAF
Table 14.1.10.1	Visit Compliance	SAF
Figure 14.1.10.2	Kaplan-Meier curves of the time to completion or discontinuation of the trial	SAF
Table 14.2.1	Changes in scores on the Mini-Mental State Examination (MMSE)	EVAL, PPROT
Table 14.2.2	Changes in scores on the 11-item Alzheimer's Disease Assessment Scale-Cognitive Subscale (ADAS-Cog/11)	EVAL, PPROT
Table 14.2.3	Changes in scores on the Grooved Pegboard Test	EVAL, PPROT
Table 14.2.4	Changes in scores on the Category Fluency Test	EVAL,

Number	Title	Population
	(CFT)	PPROT
Table 14.2.5	Changes in the Clinical Dementia Rating Scale – Sum of Boxes (CDR-SOB)	EVAL, PPROT
Table 14.2.6.1	Changes in the Alzheimer’s Disease Cooperative Study – Activities of Daily Living23 (ADCS-ADL23) for Subjects	EVAL, PPROT
Table 14.2.6.2	Changes in the Alzheimer’s Disease Cooperative Study – Activities of Daily Living23 (ADCS-ADL23) for Partners	EVAL, PPROT
Table 14.2.7	Changes on the Alzheimer’s Disease Cooperative Study – Clinical Global Impression of Change (ADCS-CGIC)	EVAL, PPROT
Table 14.2.8	Change on the Neuropsychiatric Inventory Questionnaire (NPI-Q)	EVAL, PPROT
Table 14.3.1.1.1	Overall Summary of Treatment-Emergent Adverse Events (TEAE)	SAF
Table 14.3.1.1.2	Overall Summary of Treatment-Emergent Adverse Events (TEAE) in Period 1	SAF
Table 14.3.1.1.3	Overall Summary of Treatment-Emergent Adverse Events (TEAE) in Period 2	SAF
Table 14.3.1.2.1.1	Incidence of Treatment-Emergent Adverse Events (TEAEs) by MedDRA System Organ Class and Preferred Term	SAF
Table 14.3.1.2.1.2	Incidence of Treatment-Emergent Adverse Events (TEAEs) by MedDRA Preferred Term	SAF
Table 14.3.1.2.2.1	Incidence of Treatment-Emergent Adverse Events (TEAEs) by MedDRA System Organ Class and Preferred Term in Period 1	SAF
Table 14.3.1.2.2.2	Incidence of Treatment-Emergent Adverse Events (TEAEs) by MedDRA Preferred Term in Period 1	SAF
Table 14.3.1.2.3.1	Incidence of Treatment-Emergent Adverse Events (TEAEs) by MedDRA System Organ Class and Preferred Term in Period 2	SAF
Table 14.3.1.2.3.2	Incidence of Treatment-Emergent Adverse Events (TEAEs) by MedDRA Preferred Term in Period 2	SAF
Table 14.3.1.3.1	Incidence of Treatment-Emergent Adverse Events (TEAEs) by Severity and MedDRA System Organ Class and Preferred Term	SAF
Table 14.3.1.3.2	Incidence of Treatment-Emergent Adverse Events (TEAEs) by Severity and MedDRA System Organ Class and Preferred Term in Period 1	SAF
Table 14.3.1.3.3	Incidence of Treatment-Emergent Adverse Events (TEAEs) by Severity and MedDRA System Organ Class and Preferred Term in Period 2	SAF

Number	Title	Population
Table 14.3.1.4.1	Incidence of Treatment-Emergent Adverse Events (TEAEs) by Relationship to Study Drug and MedDRA System Organ Class and Preferred Term	SAF
Table 14.3.1.4.2	Incidence of Treatment-Emergent Adverse Events (TEAEs) by Relationship to Study Drug and MedDRA System Organ Class and Preferred Term in Period 1	SAF
Table 14.3.1.4.3	Incidence of Treatment-Emergent Adverse Events (TEAEs) by Relationship to Study Drug and MedDRA System Organ Class and Preferred Term in Period 2	SAF
Table 14.3.1.5.1	Incidence of Serious Treatment-Emergent Adverse Events (TEAEs) by MedDRA System Organ Class and Preferred Term	SAF
Table 14.3.1.5.2	Incidence of Treatment-Emergent Adverse Events (TEAEs) of Special Interest by MedDRA System Organ Class and Preferred Term	SAF
Table 14.3.1.5.3	Incidence of Treatment-Emergent Adverse Events (TEAEs) Leading to Subject Withdrawal by MedDRA System Organ Class and Preferred Term	SAF
Table 14.3.1.5.4	Incidence of Treatment-Emergent Adverse Events (TEAEs) Leading to Death by MedDRA System Organ Class and Preferred Term	SAF
Table 14.3.1.6.1	Listing of Serious Treatment-Emergent Adverse Events (TEAEs)	SAF
Table 14.3.1.6.2	Listing of Treatment-Emergent Adverse Events (TEAEs) of Special Interest	SAF
Table 14.3.1.6.3	Listing of Treatment-Emergent Adverse Events (TEAEs) Leading to Subject Withdrawal	SAF
Table 14.3.1.6.4	Listing of Treatment-Emergent Adverse Events (TEAEs) Leading to Death	SAF
Table 14.3.1.7.1	Incidence of Treatment-Emergent Adverse Events (TEAEs) for Preferred Terms Associated with Blood Pressure Changes by MedDRA System Organ Class and Preferred Term	SAF
Table 14.3.1.7.2	Incidence of Treatment-Emergent Adverse Events (TEAEs) for Preferred Terms Associated with Blood Pressure Changes by MedDRA System Organ Class and Preferred Term in Period 1	SAF
Table 14.3.1.7.3	Incidence of Treatment-Emergent Adverse Events (TEAEs) for Preferred Terms Associated with Blood Pressure Changes by MedDRA System	SAF

Number	Title	Population
	Organ Class and Preferred Term in Period 2	
Table 14.3.2.1.1	Changes in hematology measurements	SAF
Table 14.3.2.1.2	Changes in serum chemistry measurements	SAF
Table 14.3.2.1.3	Changes in urinalysis measurements	SAF
Table 14.3.2.2	Frequency of categorical laboratory assessments	SAF
Table 14.3.2.3.1	Shift Table in hematology measurements	SAF
Table 14.3.2.3.2	Shift Table in serum chemistry measurements	SAF
Table 14.3.2.3.3	Shift Table in urinalysis measurements	SAF
Table 14.3.3.1	Changes from baseline in vital sign measurements and weight	SAF
Table 14.3.3.2	Changes from pre-dose in vital sign measurements within each infusion day	SAF
Table 14.3.3.3	Blood pressure measurements of special interest	SAF
Table 14.3.4.1	Changes from baseline in ECG measurements	SAF
Table 14.3.4.2	Frequency of overall ECG results	SAF
Table 14.3.5.1	Frequency of abnormal physical examination results	SAF
Table 14.3.5.2	Shift Table in physical examination results	SAF
Table 14.3.6	Frequency of Columbia-Suicide Severity Rating Scale (C-SSRS) Since Last Visit	SAF

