4.2 STUDY ENDPOINTS

4.2.1 PRIMARY ENDPOINTS

The primary endpoints in this study pertain to the safety, tolerability and feasibility of each dose level.

Safety endpoints are as follows:

- Incidence of treatment-emergent adverse events (AEs) identified by MedDRA preferred term (PT) and grouped by MedDRA System Organ Class (SOC).

Tolerability endpoints are as follows:

- Number of subjects completing 8 weeks (i.e. through Visit 10) after receiving at least 5 infusions.
- Number of subjects completing 24 weeks (i.e. through End of Study) after receiving at least 10 infusions.

Feasibility endpoints are as follows:

- Number of subjects completing 5 and 10 infusions.

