2.4 Analysis Sets

- Screened set (SCRN): All subjects who were screened and entered into EDC.
- Screen Failure set (SCRf): All subjects who were entered as screen failures in the EDC.
- Intention-to-Treat Dataset (ITT): All subjects who were randomized.
- Safety set (SAF): All subjects who received at least one dose of the study agent.
- Evaluable set (EVAL): All subjects who received at least 5 of the 10 planned doses.
- Per Protocol set (PPROT): A subset of the Evaluable set comprised of subjects who do not have any of the deviations listed below or any other deviation affecting efficacy identified prior to database lock.

Deviation Type	Deviation	Additional Clarification
Eligibility Inclusion Criteria Not Met	Diagnosis of probable AD based upon the National Institute on Aging-Alzheimer's Association (NIA-AA) Criteria	Subjects with a clinical diagnosis of AD according to NIA-AA criteria who have a negative amyloid PET scan will also be excluded.
Eligibility Inclusion Criteria Not Met	MMSE Score 12-24 inclusive	
Eligibility Inclusion Criteria Not Met	Modified Hachinski Ischemia Scale (MHIS) score of ≤ 4	
Eligibility Exclusion Criteria Met	Evidence of clinically relevant neurological disorder(s) other than AD	
Eligibility Exclusion Criteria Met	Initiation or change in the dosage of cholinesterase inhibitors (AChEI), memantine, Axona, vitamin E supplementation, or selegiline within 3 months prior to screening	Will be determined based upon actual date of change and proximity to screening. Will be determined prior to database lock
Eligibility Exclusion Criteria Met	Treatment with any human blood product, including transfusions and IV immunoglobulin, during the 6 months prior to screening	
Eligibility Exclusion Criteria Met	Concurrent daily treatment with benzodiazepines, long-acting opioids, or other medications that, in the investigator's opinion, interfere with cognition	
Eligibility Exclusion Criteria Met	Concurrent participation in another interventional clinical trial. Prior clinical trial subjects must have been off study agents for at least 30 days (or 5 half-lives, whichever is longer), 4 months for disease modifying therapies, and 1 year for vaccine or immunotherapy trials prior to screening.	

Deviation Type	Deviation	Additional Clarification

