6 SAFETY

All safety analyses will be done on the Safety Set.

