6.1.3 Period Allocation of AE

Adverse events are allocated to a period based on their start date and time. If the start date and time of an event falls between (or on) the start and stop date and time of a period, the AE is attributed to that period (treatment-emergent principle).

Rule: period start datetime \leq AE start datetime \leq period stop datetime.

In case of partial AE start dates and or times, the events are allocated to the periods using the available partial information on start and end datetime; no imputation will be done. If, for instance, for the AE start date only month and year are available, these data are compared to the month and year information of the periods. This rule may lead to multiplication of the event as a consequence of its assignment to multiple periods. In case of a completely missing AE start date, the event is allocated to the first period, except if the end date of the AE falls before the start of this period. In case of any other missing scenarios, the period allocation of AE will be determined by manual data review prior to database lock.

6.1.4 Variables Attributed to Adverse Events:

- AE term (verbatim and MedDRA preferred term and system organ class)
- Onset datetime, End datetime, and duration of AE
- Serious AE (Yes/No), if yes classification will be listed
- Severity (Mild, Moderate, Severe)
- Relation to study treatment (Unrelated, Possibly Related, Definitely Related)
- Frequency (Single Episode, Intermittent, Continuous)
- Action taken with study treatment (No Action Taken, Treatment Held, Treatment Discontinued)
- Other Action due to AE (Medication Therapy, Non-Drug Therapy, Other)
- Outcome of AE (Recovered/Resolved, Not Recovered/Not Resolved, Resolved/Resolved with Sequelae, Fatal, Unknown)
- AE leading to death (Yes/No)
-
- AE of special interest

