6.1.5 Analysis Methods

There will be no formal statistical testing unless indicated otherwise.

A summary will be provided for the following TEAEs per period and overall (Table 14.3.1.1.1-14.3.1.1.3):

- Subjects with Any TEAE
- Subjects with Any Study Drug-Related¹ TEAE
- Subjects with Any TEAE with an Outcome of Death
- Subjects with Any Serious TEAE
- Subjects with Any Study Drug-Related Serious TEAE
- Subjects with Any TEAE Leading to Discontinuation of Study Drug
- Subjects with Any Study Drug-Related TEAE Leading to Discontinuation of Study Drug
- Subjects with Any TEAE of Special Interest
- Subjects with Any Study Drug-Related TEAE of Special Interest

The adverse events will be shown by MedDRA system organ class and preferred term, in order of descending overall frequency. For each AE, the percentage of subjects who experience at least 1 occurrence of the given event will be summarized per period and overall. Incidence tabulations will be provided for overall summary (Table 14.3.1.2.1-14.3.1.2.3), summary by highest severity (Table 14.3.1.3.1-14.3.1.3.3), and summary by relatedness (Table 14.3.1.4.1-14.3.1.4.3).

Incidence of Serious TEAEs, TEAEs of Special Interest, TEAEs Leading to Subject Withdrawal and TEAEs Leading to Death will be tabulated by MedDRA System Organ Class and Preferred Term (Table 14.3.1.5.1-14.3.1.5.4), and listed as well (Listing 14.3.1.6.1-14.3.1.6.4).

Adverse events with preferred terms associated with blood pressure changes will also be presented by infusion period, SOC, PT, and treatment group. Infusion

period will be further categorized by whether the event start date occurred during the infusion period or after the infusion period. Examples of such events can be identified by the following preferred terms: blood pressure decreased, blood pressure diastolic decreased, blood pressure systolic decreased, blood pressure increased, increased blood pressure, blood pressure diastolic increased, blood pressure systolic increased, hypotension, hypertension, low blood pressure, high blood pressure. This is a non-exhaustive list and a review of AE MedDRA coding will be conducted prior to lock to identify all events associated with blood pressure changes. (Table 14.3.1.7.1-14.3.1.7.3).

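### The SAP's Period 2 adverse-event tables use the whole Safety Set, so subjects never infused in the second course dilute the second-course rates

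*SAP*

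**What the plan says.** SAP Section 10 lists six TEAE tables for Period 2: 14.3.1.1.3, 14.3.1.2.3.1, 14.3.1.2.3.2, 14.3.1.3.3, 14.3.1.4.3 and 14.3.1.7.3. Two of the titles are "Overall Summary of Treatment-Emergent Adverse Events (TEAE) in Period 2" and "Incidence of Treatment-Emergent Adverse Events (TEAEs) by MedDRA Preferred Term in Period 2". The Population column reads SAF for all six.

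The text agrees with the table list:

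- SAP 6 makes no exception by period: "All safety analyses will be done on the Safety Set".
- SAP 2.4 defines the Safety Set as "All subjects who received at least one dose of the study agent". It has no Period 2 dosing condition.
- SAP 6.1.5 names the statistic: "the percentage of subjects who experience at least 1 occurrence of the given event will be summarized per period and overall".
- SAP 6.1.3 fixes which events count: "Adverse events are allocated to a period based on their start date and time".

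No readable passage limits the Period 2 denominator to subjects infused in Period 2. The SAP does write denominator exceptions where it wants them: in 4.3 for declined or unknown answers, and in 6.5 for physical examinations that were not done.

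**The concern.** The numerator is specific to the period and the denominator is not. A subject who had the first course and no more was never exposed to the second, yet will normally count in the Period 2 table as a treated subject without an event.

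The plan expects such subjects. Protocol 10.4.5 proposes to compare those who finish both series with those who finish only the first. SAP 4.7 tabulates subjects by number of infusions completed, including 1-4 and exactly 5.

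The loss may also be informative. Protocol 5.4.1 withdraws subjects for a TEAE judged to be an unacceptable risk, so a subject who leaves because of a first-course event would help to make the second course look well tolerated. Tolerability on re-exposure is the natural reason to show Period 2 separately. If the arms lose different numbers, the dilution differs by dose.

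**Working it through.** **Inputs**

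- Planned size: 20 subjects per arm, 40 in all (SAP 1.3; Protocol 10.5).
- Drop-out: 25% (Protocol Summary, Population).
- Population for the Period 2 TEAE tables: SAF (SAP 10).
- Number infused in Period 2 (n2): not given, so a range is used.

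**The plan's own figure.** 40 x (1 - 0.25) = 30, which matches the roughly 30 evaluable subjects stated. Protocol 10.5 ties evaluability to at least 5 doses and completion through Visit 8, which is Day 6. The 25% is therefore not a Period 2 entry rate. Using it as the upper end of the range (20 x 0.25 = 5 lost per arm) is an assumption.

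**Formula.** Let x be the number of Period 2-infused subjects with the event.

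- Printed rate = x / N_SAF
- Rate among those infused in Period 2 = x / n2
- Printed rate / infused rate = n2 / N_SAF

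**Per arm, N_SAF = 20**

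| Lost before Period 2 | n2 | Factor | x = 3: printed, infused | x = 6: printed, infused |
|---|---|---|---|---|
| 0 | 20 | 1.00 | 15.0%, 15.0% | 30.0%, 30.0% |
| 2 | 18 | 0.90 | 15.0%, 16.7% | 30.0%, 33.3% |
| 5 | 15 | 0.75 | 15.0%, 20.0% | 30.0%, 40.0% |

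**Period 1 against Period 2.** Suppose 8/20 = 40% have an event in Period 1 and 6/15 = 40% of those infused have one in Period 2. The Period 2 table shows 6/20 = 30%, an apparent fall of 10 points with no change in the rate.

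**Between doses (illustration only; the documents give no loss by arm).** With an expected 40% among infused subjects in both arms, and 19 infused in one arm against 15 in the other, the expected printed rates are 0.40 x 19/20 = 38% and 0.40 x 15/20 = 30%. That is an 8-point difference from the denominator alone. These are expectations, not counts that a table would show.

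**Two things move the factor.**

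- SAP 1.3 allows replacement of subjects who leave before Visit 8. Those already dosed remain in SAF, so N_SAF can exceed 20 and the factor falls further for a given n2.
- SAP 6.1.3 allocates events by period start and stop, which the readable text does not define. If Period 2 runs by calendar, an uninfused subject still in follow-up could add an event to the numerator, and the dilution would be smaller.

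**The case against.** **The divisor is never written out.** The Population column names an analysis set, and SAP 6.1.5 says percentage of subjects without giving the denominator. The mock shells are a separate document (SAP 1) and could carry a Period 2 N; Section 10 also lets the sponsor approve changes. This stands as a limit on certainty. But SAP 1 says the shells serve programming according to the finalized SAP, and the SAP names SAF with no exception.

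**The primary endpoint is not touched.** A reader might infer that the primary safety result is understated. The documents do not support that. Protocol 4.2.1 defines TEAE incidence without a period split. The overall tables are unaffected, and so are the Period 1 tables, because under the schedule every SAF subject was dosed in Period 1. The serious, special-interest, withdrawal and death tables (14.3.1.5.1 to 14.3.1.5.4) are not split by period. SAP 6.1.5 plans no formal AE testing unless stated otherwise, and no confidence interval for AE rates, so no misleading bound would be printed.

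**An uninfused subject can still have a Period 2 event.** It is tempting to say that this is impossible. It is not: SAP 6.1.2 follows TEAEs to the end of follow-up, SAP 4.1 separates stopping study drug from stopping the study, and SAP 6.1.3 can place a partially dated event in more than one period. A fix to the denominator alone could then leave an event whose subject is not in the denominator.

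**A reader could reconstruct the rate.** Exposure is summarized per period and infusion parameters per infusion day (SAP 4.6), so n2 should be recoverable. That softens the harm, but the printed percentage remains the one that will be quoted.

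**Restricting to infused subjects has its own selection.** It conditions on continuing after the first course, so the doses are no longer compared as randomized. This is correct and belongs in a footnote. The SAF percentage does answer a question (of all treated, what share had an event in Period 2), but it is not a second-course rate.

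**Conclusion.** The point holds for the six Period 2 TEAE tables. As written, they divide second-course events by all subjects ever dosed, and so understate the rate among those given the second course by about n2/N_SAF. Per arm of 20, the factor runs from 1.00 (no effect) with 0 lost, through 0.90 with 2 lost, to 0.75 with 5 lost. Where in that range the trial falls is unknown, because the documents do not give the number missing Period 2.

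The conclusion assumes that the Population column sets the denominator and that Period 2 events come essentially from subjects infused in Period 2. It concerns a descriptive breakdown. It should be corrected before database lock, but it does not undermine the primary safety analysis.

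**What to change.** In SAP 6.1.5 and Section 10:

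- Base both numerator and denominator of the six Period 2 TEAE tables on SAF subjects with at least one Period 2 infusion.
- Count these subjects' events with onset from their first Period 2 infusion, and state that boundary in 6.1.3.
- Print the resulting N by dose in the column headers.
- Keep SAF for the overall and Period 1 tables, so that an event in an uninfused subject still appears in the overall tables.

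The cost is a short addition to the text, one population flag and a header N, and Section 10 already allows modification with sponsor approval. The downside is that the two periods have different Ns and that Period 2 subjects are those who continued after the first course. A footnote should give that caveat for comparisons between periods and between doses.
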